It is now clear that immunosuppressive strategies for renal transplantation achieve excellent short-term and medium-term results. Unfortunately, the long-term results have not substantially improved in the last 20 years. The reasons for this failure to achieve better long-term results are complicated and include such things as allowing older and sicker people to be recipients, using poorer quality donor kidneys and the complications associated with long-term immunosuppression. Among the worst of the long-term effects of chronic immunosuppression are the nephrotoxicity of the calcineurin inhibitors and the myriad complications of steroids. The goal of many now in the transplant field is to limit the exposure of transplant recipients to both steroids and calcineurin inhibitors. The following protocol evaluates the reduction of calcineurin inhibitors in a protocol that has already successfully eliminated the long-term use of steroids. Given the substantial experience with Campath® detailed above, the following study protocol will be offered to all patients undergoing renal transplantation at the University of Toledo University Medical Center. This is a small pilot study; multiple comparisons will be made for descriptive purposes only.

Hypothesis:

Our hypothesis is that conversion to everolimus (Zortress®), allowing the reduction of calcineurin inhibitors, will reduce nephrotoxicity (measured by increased creatinine clearance) and lengthen overall graft survival (measured by 2-year graft survival).

Objectives:

1. The primary objective of the study is to compare the efficacy and the effects on renal function of calcineurin-inhibitor reduction with conversion at 2 months after transplantation to Reduced Dose tacrolimus/everolimus in adult renal transplant recipients. Efficacy will be defined using two co-primary endpoints.
 - a. A composite efficacy end point [treated biopsy-proven rejection (BPAR), graft loss, death or loss to follow-up].
 - b. Renal function at 24 months post transplantation using GFR as measured by the Modified Diet Renal Disease (MDRD) estimation.

2. Secondary objectives will be to:
 - a. Compare the safety and tolerability of the experimental arm compared to the historical control arm.
 - b. Compare the presence of proteinuria as defined by spot urine protein to creatinine ratio greater than 1.0 in the experimental arm to the historical control arm.

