 - c. Compare the presence of hyperlipidemia in the experimental arm to the historical control arm.
 - d. Compare the incidence of impaired glucose tolerance (IGT) as assessed by fasting blood sugar, HbA1c and need for hypoglycemic medications in the experimental arm to the historical control arm.
 - e. Compare the incidence of mouth ulcers in the experimental arm to the historical control arm.
 - f. Compare the incidence of GI complaints including diarrhea in the experimental arm to the historical control arm.
 - g. Compare the incidence of leukopenia as defined by WBC less than 1.0, absolute neutrophil count less than 500 or the need for exogenous granulocyte stimulating factor administration in the experimental arm to the historical control arm.
 - h. Compare the incidence of thrombocytopenia at one year as defined by platelet count less than 50 or need to discontinue one of the study medications for more than 30 days in the experimental arm to the historical control arm.
 - i. Compare the incidence of neurotoxicity as defined by incidence of new onset seizure activity or tremors in the experimental arm to the historical control arm.
 - j. Compare the incidence of pneumonitis in the experimental arm to the historical control arm.
 - k. Compare the incidence of serious infections as defined by need for hospitalization in the experimental arm to the historical control arm.
 - l. Compare the incidence of CMV infection as defined by need for hospitalization in the experimental arm to the historical control arm.
 - m. Compare the incidence of BK infection as defined by blood titers requiring reduction in immunosuppressive dose in the experimental arm to the historical control arm.

n. Compare the incidence of BK nephropathy as defined by biopsy in the experimental arm to the historical control arm. Note that biopsies will not be required as part of the study but will only be done as part of the patient's standard of care if rejection is suspected (i.e. if the serum creatinine increases by 25% and is not associated with elevated tacrolimus levels or clinical signs of dehydration/illness to account for elevated creatinine).

o. Compare the incidence of malignancies including PTLN in the experimental arm to the historical control arm.

p. Compare the incidence of cardiovascular complications such as dysrhythmias, coronary artery disease requiring intervention or myocardial infarction in the experimental arm to the historical control arm.

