 - Adequate barrier methods of contraception include: diaphragm, condom (by the partner), intrauterine device (copper or hormonal), sponge or spermicide. Hormonal contraceptives include any marketed contraceptive agent that includes an estrogen and/or a progestational agent. Acceptable contraception methods will be discussed with all women of child-bearing potential.

- Reliable contraception should be maintained throughout the study and for 8 weeks after study drug discontinuation. For women who become pregnant while using Myfortic® or within 8 weeks of discontinuing therapy, we will report the pregnancy to the Mycophenolate Pregnancy Reference Registry ([name]) and will strongly encourage the patient to enroll in the pregnancy registry.
- Women are considered post-menopausal and not of child bearing potential if they have had 12 months of natural (spontaneous) amenorrhea with an appropriate clinical profile (e.g. age appropriate, history of vasomotor symptoms) or six months of spontaneous amenorrhea with serum FSH levels > 40 mIU/mL and estradiol < 20 pg/mL] or have had surgical bilateral oophorectomy (with or without hysterectomy) at least six weeks ago. In the case of oophorectomy alone, only when the reproductive status of the woman has been confirmed by follow up hormone level assessment is she considered not of child bearing potential.

Study Duration:

We plan to enroll 11 patients per year. Given this assumption, the enrollment will take five years. Adding two years of follow-up care, we will be able to complete the study in 7 years.

Study Design:

1. Single center pilot study utilizing historical control
2. A single treatment arm
3. Eleven patients per year
4. Five years to enroll 55 patients.
5. Enroll all patients who meet the inclusion criteria at 2 months and up to 6 months (± 10 days) post kidney transplantation and are willing to consent for this trial.
6. Patients would have study visits, serum creatinine measurements and other clinically relevant parameters measured monthly until 6 months, then q3 months until 2 years post-transplantation.
7. Graft survival would be measured by the absence of the need for dialysis.
8. It would not be mandatory, but a renal biopsy would be recommended at 2 years to look for underlying early signs of calcineurin toxicity/chronic allograft nephropathy.

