9. Secondary endpoints would include such parameters as post-transplant diabetes, proteinuria, lipid levels, mouth sores, neurotoxicity, pneumonitis, CMV, PTLN, BK-nephropathy, malignancies, cardiovascular complications, etc.
10. Our historical control will be composed of patients transplanted at the University of Toledo Medical Center between October 2011 and the beginning of this trial. All of those patients will have been treated with the exact same protocol as in this study except that they will not have been converted to the treatment arm above, but will have remained on tacrolimus and myfortic®, unless the clinical situation warranted changing immunosuppression. We expect that the control group will consist of approximately 50-55 patients and will have similar demographics to the patients that will be enrolled in this trial, given that we will use the same inclusion and exclusion criteria to select all patients from October 2011 until the start of this trial to populate

the historical control group. The reason for October 2011 as the starting point for the historical control is that this is the date when we modified our protocol to add a five day taper of steroids immediately after transplantation. Prior to that we only gave steroids immediately prior to the transplantation procedure. Thus, to be consistent with the patients in this trial, we believe the most accurate historical control should have the same treatment with steroids perioperatively. We will utilize all patients available in the historical control dataset and will not attempt to match for the demographics present in the experimental arm. The control group will consist of a historical control; prospective patients who are not willing to participate in the study will not be considered part of the control group.

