23. Patients who have CMV-mismatched kidneys may be followed with CMV viral titers. Patients suspected of rejection episodes due to elevated creatinine levels should also be assessed for the possibility of BK-nephropathy by following urine cytology, looking for viral inclusion bodies on electron microscopy of biopsy specimens and by following BK viral titers in urine and or blood.

Conversion at 2-6 Months (± 10 days) to the Study Protocol

1. Only patients who have reached the two month (± 10 days) post-operative mark without prior evidence of rejection will be offered the opportunity to participate in the study.
2. At the two month mark (± 10 days), patients will be counseled about participation in the study and informed consent obtained prior to participation. Our control group will consist of a historical control; prospective patients who are not willing to participate in the study will not be considered part of the control group.
3. Study participants will be maintained on the following immunosuppression regimen:
 - a. Their myfortic® will be weaned off quickly and everolimus initiated to achieve a target level of 3-8 ng/ml with a mean of 6 ng/ml. Once achieving a therapeutic dose of everolimus, the tacrolimus dose will be reduced to target a level of 3-5 ng/ml with a mean of 4 ng/ml.
 - b. As noted above, patients in the historical control group will have remained on tacrolimus and myfortic® according to the target levels outlined in #13 above. Briefly, the tacrolimus target level would be reduced to 8-10 ng/ml (with a target level of 8 ng/ml) until the end of the first year and after the first year the tacrolimus target level would be further reduced to 6-8 ng/ml (with a target level of 6 ng/ml) if no evidence of rejection had been encountered.

AE Reporting

Any suspected serious adverse event (SAE) will be reported to the Novartis drug safety and epidemiology team overseeing the study within 24 hours of investigator awareness that an SAE has occurred. An SAE report form will be completed for any serious adverse event occurring after the subject has provided informed consent and until 4 weeks after the subject has stopped study participation. A serious adverse event (SAE) report form will be faxed to the number provided by the Novartis clinical trials team.

The form will contain the following information:

Investigator contact details

Date of report
Subject description/study number / initials
Subject treatment arm

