VISIT TIME WINDOWS	2-6 Mos ± 10 days		±7 days						±14 days			±30 days			
INFORMED CONSENT	X														
BACKGROUND INFORMATION	X														
MEDICAL HISTORY	X														
INCLUSION/EXCLUSION CRITERIA	X														
TRANSPLANT INFORMATION	X														
VIRAL SEROLOGY	X														
BK VIRAL TITERS			X		X			X	X	X		X		X	
EBV VIRAL TITERS (if neg)	X							X		X		X		X	
CMV VIRAL TITERS (if neg)	X														
DSA EVALUATION	X		X		X			X		X		X		X	
PHYSICAL EXAM	X	X	X	X	X	X	X	X	X	X	X	X	X	X	
VITAL SIGNS	X	X	X	X	X	X	X	X	X	X	X	X	X	X	
PREGNANCY TEST (if applicable)	X		X		X			X	X	X		X		X	
PRIOR & CONCOMITANT MEDICATIONS	X	X	X	X	X	X	X	X	X	X	X	X	X	X	
SAFETY LABORATORY TESTS**	X	X	X	X	X	X	X	X	X	X	X	X	X	X	
SERUM CREATININE	X	X	X	X	X	X	X	X	X	X	X	X	X	X	
STUDY MEDICATION ADMINISTRATION (if applicable)		X	X	X	X	X	X	X	X	X	X	X	X	X	
EVEROLIMUS LEVEL (if applicable)			X	X	X	X	X	X	X	X	X	X	X	X	
TACROLIMUS LEVEL (if applicable)	X	X	X	X	X	X	X	X	X	X	X	X	X	X	
MYFORTIC LEVEL (if applicable)	X				X			X	X	X		X		X	
OTHER IMMUNOSUPP THERAPIES	X	X	X	X	X	X	X	X	X	X	X	X	X	X	
SUSPECTED ACUTE REJECTION RECORD	X	X	X	X	X	X	X	X	X	X	X	X	X	X	
HOSPITALIZATION RECORD			X	X	X	X	X	X	X	X	X	X	X	X	
DIALYSIS RECORD			X	X	X	X	X	X	X	X	X	X	X	X	
AE & INFECTION LOG			X	X	X	X	X	X	X	X	X	X	X	X	
SERIOUS ADVERSE EVENTS			X	X	X	X	X	X	X	X	X	X	X	X	
GRAFT LOSS			X	X	X	X	X	X	X	X	X	X	X	X	
END OF TREATMENT /END OF STUDY														X	

** Safety Labs include: Chem 13; AST, ALT, CBC w/ Diff; Lipid Profile; Magnesium, Inorganic Phosphate

References

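### Control-arm adverse events have no stated source, definitions or time window, so the mouth-ulcer, GI-complaint and tremor comparisons are prone to unequal event capture

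*Combined protocol and SAP*

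**What the plan says.** All references are to the combined protocol and SAP.

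- **Objectives.** Item 2a reads "Compare the safety and tolerability of the experimental arm compared to the historical control arm". Three of the items that follow rest on symptoms: 2e ("Compare the incidence of mouth ulcers in the experimental arm to the historical control arm"), 2f ("Compare the incidence of GI complaints including diarrhea in the experimental arm to the historical control arm") and 2i ("Compare the incidence of neurotoxicity as defined by incidence of new onset seizure activity or tremors"). None of the three has a grade, test or treatment trigger. Other items do: 2b, 2g, 2k, 2l, 2m and 2n rest on a urine ratio, blood counts or growth-factor use, hospital admission, viral titers with dose reduction, or biopsy.
- **Trial arm.** The Evaluation and Visit Schedule has a row "AE & INFECTION LOG" marked at every treatment visit. Study Design item 6 sets visits "monthly until 6 months, then q3 months until 2 years post-transplantation". Under AE Reporting, "An SAE report form will be completed for any serious adverse event occurring after the subject has provided informed consent", continuing until 4 weeks after participation ends.
- **Controls.** Study Design item 10 takes patients transplanted at the centre from October 2011 to the start of the trial: "We will utilize all patients available in the historical control dataset". It says they had the same treatment apart from the conversion. It does not say where their adverse events come from, who classifies them, under which definitions, or over which period.
- **Analysis.** Study Purpose and Rationale calls the multiple comparisons descriptive. The Statistical Section allows a summary of AEs and SAEs by group, without tests. The only drawback it attaches to the historical control is weaker statistical significance. It also says the data will be published whatever the result and will be available for meta-analysis.

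**The concern.** Asking patients at fixed visits tends to find more mild complaints than reading back through routine notes, even when the true rates are equal. The trial arm is documented as prospective. The controls predate the trial and have no study visits, consent or log, so their events presumably come from routine records.

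If so, part of any excess of mouth ulcers, GI complaints or tremor on everolimus could reflect how events were collected. A real tolerability gain could also be hidden. Leaving out significance tests does not remove this, because rates printed side by side will be read as a comparison and may be pooled elsewhere. Unequal event capture is not mentioned anywhere in the plan.

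**Working it through.** **The plan's own figures.** Trial-arm size: 11 patients per year x 5 years = 55, as stated. Duration: 5 + 2 = 7 years, as stated. The expected control group is about 50-55. The plan gives no adverse event rate, capture rate, alpha or power, so there is nothing further to reproduce.

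**Log visits.** Months 1 to 6 (six visits) plus months 9, 12, 15, 18, 21 and 24 (six visits) = 12 in the trial arm. None is described for controls.

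**Effect of unequal capture.** Apparent rate = true risk x probability that an event is recorded. All risks and capture probabilities below are assumptions, and the true risk is the same in both arms.

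| True risk | Log capture | Control capture | Trial rate | Control rate | Apparent ratio |
|---|---|---|---|---|---|
| 15% | 90% | 70% | 13.5% | 10.5% | 1.29 |
| 15% | 90% | 40% | 13.5% | 6.0% | 2.25 |
| 20% | 100% | 80% | 20% | 16% | 1.25 |
| 20% | 100% | 70% | 20% | 14% | 1.43 |
| 20% | 100% | 50% | 20% | 10% | 2.00 |

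The true risk cancels from the ratio: 0.90/0.40 = 2.25 and 1/0.80 = 1.25. If capture were nearly equal (95% against 90%), the ratio would be only 0.95/0.90 = 1.06.

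At 20% true risk the false difference is +4, +6 or +10 points at 80%, 70% or 50% control capture. With 55 per arm, the 95% half-width is 1.96 x sqrt[a(1-a)/55 + c(1-c)/55], where a and c are the apparent trial and control rates. For 20% against 16% this is 14.3 points; for 20% against 10% it is 13.2 points. If a reader applied a two-sided 5% test, the chance of a significant result against everolimus would be about 8%, 13% and 31%, compared with 2.5% without bias. Over true risks of 10-40% and control capture of 50-80%, the false difference runs from +2 to +20 points.

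**A hidden benefit.** Suppose the true risk is 30% in controls and 20% on everolimus, with full log capture. The arms look equal when 0.30 x s = 0.20, that is, at control capture s = 67%.

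**The opposite direction.** The control counting window is undefined. Trial patients enter 2 to 6 months after transplant, so the log misses the earlier period. Assume a constant hazard, a 20% risk over 24 months, control counting from transplant, and trial counting only from entry to month 24 after transplant:

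- Entry at month 2: 1 - 0.80^(22/24) = 18.5%.
- Entry at month 6: 1 - 0.80^(18/24) = 15.4%.

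The control rate would be 20% x s, where s is control capture. With full log capture, the window effect outweighs the capture effect when s exceeds 18.5/20 = 92% (entry at month 2) or 15.4/20 = 77% (entry at month 6). The sign of the net bias is therefore not fixed by the documents.

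The end of the trial window is not clear either. Study Design item 6 counts to 2 years after transplant, while the visit schedule numbers its months within a treatment period that follows a baseline visit.

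**The case against.** The strongest reply has five parts.

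- **Source.** A reader might infer that the protocol says control events come from charts. It does not; it names only a dataset. The inference is strong, because the controls predate the trial and the centre's earlier comparison in Background and Preliminary Data was assembled retrospectively, but it remains an inference.
- **Direction.** A reader might also infer that the bias must run against everolimus. The undefined window prevents that conclusion. Control counting from transplant would include the early months on standard care, with their higher tacrolimus targets, which the trial log never covers.
- **Scope.** It is tempting to extend the point to all of 2a. Many items are anchored to a laboratory value, admission or biopsy, and seizure in 2i is a hard event. Diarrhea in controls was a reason to lower myfortic (Brief Immunosuppressive Management, item 2), so clinically relevant diarrhea probably left a record. The exposed endpoints are mouth ulcers, milder GI complaints and tremor.
- **Consequence.** The comparisons are descriptive and untested, no decision rule rests on them, and most of the illustrated gaps are smaller than the sampling error. This limits the seriousness. It does not correct the published rates.
- **Remedy.** Complaints raised at study visits may enter trial patients' clinic notes, so using charts for both arms reduces the imbalance without removing it. That is true, and it is why comparative conclusions should rest on objective events.

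**Conclusion.** The point holds in limited form. Collection is documented as prospective in one arm and left unspecified in the other. That makes 2e, 2f and the tremor part of 2i prone to unequal ascertainment, probably to the disadvantage of everolimus.

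The documents give no basis for estimating the size. Under the two sets of assumed capture rates (90% against 40-70%, and 100% against 50-80%), a true ratio of 1 would appear as about 1.3 to 2.3. It would be close to 1 if capture were nearly equal, and it could reverse if control events are counted from transplant. The documents do not support a claim that everolimus will certainly look worse, or that the whole safety comparison is invalid.

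**What to change.** State the source, definitions and counting window for control adverse events. Then:

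1. For every between-arm safety table, abstract both arms from routine medical records, using one form, one set of definitions, and the same start and end time after transplant.
2. Base comparative conclusions on events with objective evidence: admission, laboratory value, biopsy, or a new drug started.
3. Report log-derived mouth ulcers, GI complaints and tremor separately for the trial arm. Label any control figure for these as chart-derived and not comparable with the log.
4. Keep the log, SAE and hospitalization records as the basis for the trial arm's own safety reporting.

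The cost is abstraction of up to 55 trial charts at the same centre, on the form needed for the controls in any case. Counts in the comparative tables will be less complete than the log, and some bias will remain if complaints raised at study visits reach the trial charts. Giving up a firm comparison on the three symptom endpoints is a debatable trade-off, and the plan should state it openly. Overall this is a cheap improvement.

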After publication of the study by Hanaway et al. in NEJM in late 2011, we decided that our 15-20% rejection rate with Prograf® and myfortic® with no steroid taper was unacceptable.¹⁸ Therefore, we modified our protocol to eliminate the second dose of 500 mg methylprednisolone intraoperatively and instead have spread this out by adding a steroid taper for the first five days post-operatively as was done in the Hanaway study. Since adopting this policy, we have seen a significant reduction in our rejection rate.

Everolimus (Zortress®) inhibits the proliferation (growth or production) of T and B cells. It is an inhibitor of intracellular signal transduction (the relaying of signals inside a cell that communicates to the cell that it should activate or change) that targets the

mammalian target of rapamycin (mTOR). The mechanism of action of everolimus appears to be distinct from those of calcineurin inhibitors. It forms a complex with the cytoplasmic protein FKBP-12 (intracellular tacrolimus-binding protein) and binds to and interferes with the function of FRAP. FRAP is a key regulatory protein which governs cell metabolism, growth and proliferation. The blockage of this signal leads to inhibition of cell cycle progression from G1 to the S phase (cell cycle growth phases); thus not allowing cells to develop and multiply. Combining everolimus and a calcineurin inhibitor gives rise to synergistic immunosuppressive properties.

Tacrolimus (Prograf® or Hecoria®) inhibits T-lymphocyte activation, although the exact mechanism of action is not known. Experimental evidence suggests that tacrolimus binds to an intracellular protein, FKBP-12. A complex of tacrolimus-FKBP-12, calcium, calmodulin, and calcineurin is then formed and the phosphatase activity (enzyme that frees or removes phosphate from a chemical reaction) of calcineurin is inhibited. This effect may prevent the dephosphorylation (removal of a phosphate group) and translocation (chromosome rearrangement) of nuclear factor of activated T-cells (NF-AT), a nuclear component thought to initiate gene transcription for the formation of lymphokines (substances released by activated T-cells such as interleukin-2 or gamma interferon). The net result is the inhibition of T-lymphocyte activation (i.e., immunosuppression).

Study Purpose and Rationale

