12. If delayed graft function is suspected, tacrolimus may be held for the first few days until the creatinine level begins to fall spontaneously.
13. Target tacrolimus levels for the first 2 months post-operatively will be 10-12 ng/ml with a target level goal of 10 ng/ml. After three months, the standard of care approach calls for the tacrolimus target level to be reduced to 8-10 ng/ml (with a target level of 8 ng/ml) until the end of the first year. After the first year, patients without evidence of rejection would have their tacrolimus dose reduced to achieve a trough level of 6-8 ng/ml (with a target level of 6 ng/ml). This approach was used for patients in the historical control arm.
14. No patients are to be treated for rejection without first obtaining a renal biopsy to confirm a cellular or humoral rejection.
15. Cellular rejections scored as Banff 1 will be treated with three, daily pulses of 250-500 mg methylprednisolone on three consecutive days and by confirming a therapeutic level of tacrolimus. Cellular rejections scored as Banff 2 or for those rejections that are not responsive to steroids alone, Thymoglobulin® will be used for a 10-14 day course. Depending on the level of rejection,

- ongoing steroid therapy can be administered after agreement by the treating physicians. Generally, hospitalization is required for at least the first few days of the treatment of rejection using Thymoglobulin®. During the first dose of Thymoglobulin®, blood pressure and vital signs will be monitored every 15 minutes for the first hour, then every 30 minutes for the next two hours, then every one hour for the next 3 hours and then per routine protocol if stable.
16. Humoral rejections will be treated with IVIG 100 mg/kg followed by a one volume exchange plasmapheresis on an every other day basis until the creatinine begins to fall or a decision is made to hold off on further treatment. In extreme cases, re-dosing Campath® can be considered or use of the anti-B cell agent, Rituximab (anti-CD20) can be used. These decisions will be made after consultation between the transplant surgeon and attending nephrologists.
 17. The intention-to-treat concept will be applied to patients who experience biopsy-proven rejection to avoid missing outcomes. For patients in the study, low-dose myfortic® may be added back to the patient's immunosuppression regimen. Short-term treatment with oral corticosteroids may be required, but long-term steroid use will be avoided.

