 18. For patients with elevated, post-transplant creatinine but without biopsy proven evidence of cellular or humoral rejection, causes of elevated creatinine other than rejection should be considered. These include intercurrent illness, dehydration, BK-nephropathy and tacrolimus toxicity. Dose reduction of tacrolimus can be attempted to assess for the possibility of calcineurin-inhibitor nephrotoxicity. If dose reduction of tacrolimus is not acceptable, then everolimus (first choice) or Neoral® (second choice) will be used as replacement therapy.
 19. Upon discharge from the hospital, all patients will be treated with the following prophylactic medications:
 - a. Valcyte® 450 mg PO daily to prevent subsequent CMV infection (unless leukopenia or other side effects warrant further dose reduction or discontinuation). Valcyte® will be administered for 6 months if there is no CMV mismatch and for 12 months if there is a CMV mismatch.
 - b. Bactrim DS® one tablet PO Monday, Wednesday and Friday to prevent subsequent pneumocystis carinii pneumonia. In hospital desensitization with [name] can be performed if the patient has a known sulfa allergy or Dapsone replacement can be used. Bactrim® will be administered for at least one year following transplantation. Length of therapy after one year will be determined by physician and patient preference.
 - c. Mycelex® Troche one lozenge PO QID to prevent oral thrush. Mycelex troche® therapy will be continued for 6 months post-transplantation.
 - d. Flagyl® 500 mg PO TID to prevent Clostridium difficile infection only during in-hospital stays of transplant patients.
 20. BK viral titers will be assessed at three month intervals for the first year post-operatively.
 21. Post-transplant PRAs (to determine the presence or absence of donor specific antibodies – DSA) will be assessed at the patient's screening visit, at three month intervals for the first year post-operatively and every 6 months in the

second year post-operatively. PRAs may also be assessed at the discretion of the principal investigator or measured as part of the patient's standard of care/routine treatment.

22. For patients who are prescribed myfortic® as part of an intention-to-treat adverse event, MPA levels will be assessed on an as needed basis.

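### Objective 2m counts BK infection only when doses are cut, so the same viremia can be a case in one arm and not in the other; a fixed titer threshold at shared test times would repair it

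*Combined protocol and SAP*

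**What the plan says.** Objective 2m is to "Compare the incidence of BK infection as defined by blood titers requiring reduction in immunosuppressive dose" between the experimental and historical control arms. It states no titer threshold, no assay, no time window and no rule for what counts as a reduction. Nearby objectives do carry numbers: a protein-to-creatinine ratio above 1.0 in 2b, WBC and neutrophil limits in 2g, a platelet limit in 2h.

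The regimens differ at the point where the decision is made. For trial patients, Conversion at 2-6 Months, item 3a, says: "Their myfortic® will be weaned off quickly and everolimus initiated to achieve a target level of 3-8 ng/ml with a mean of 6 ng/ml". Afterwards "the tacrolimus dose will be reduced to target a level of 3-5 ng/ml with a mean of 4 ng/ml". Controls stayed on myfortic. For their tacrolimus, item 13 of the Detailed Renal Transplantation Immunosuppression and Management Protocol says: "After three months, the standard of care approach calls for the tacrolimus target level to be reduced to 8-10 ng/ml", with a further step to 6-8 ng/ml after the first year.

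BK testing appears in two places. Item 20 of the same section says: "BK viral titers will be assessed at three month intervals for the first year post-operatively". In the Visit Schedule, the row "BK VIRAL TITERS" is marked at Months 1, 3, 6, 9, 12, 18 and 24 and is blank at Screening and Baseline. DSA, EBV and CMV all have a Screening entry.

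**The concern.** An infection rate compared between arms should mean the same thing in each. Here a patient becomes a case only if someone acts on the titer. In the trial arm that person knows the treatment and works under Study Design item 11, which ends study treatment permanently if everolimus or tacrolimus is interrupted for more than 14 consecutive days. For controls the action is abstracted from earlier routine care, where Study Design item 10 allowed immunosuppression to change as the clinical situation required. The drugs and levels open to reduction also differ.

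The missing entry titer is a second, smaller matter. Without it, viremia found soon after conversion cannot be divided into pre-existing and new.

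At stake is whether a difference in 2m, or the lack of one, says anything about the regimens. The Statistical Section intends the data to be published for use in meta-analysis, so a rate that means different things in the two arms would be carried forward.

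**Working it through.** **1. Figures in the plan.** There is no BK rate, effect size, alpha or power to reproduce. The only arithmetic, 11 patients a year × 5 years = 55, is consistent.

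**2. Effect of the definition.** Observed rate = true viremia rate × share of viremic patients whose doses are cut because of the titer. All inputs below are assumptions, with the true rate equal in both arms.

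| True rate, both arms | Control at 80% acted on | Trial at 60% | Trial at 40% | Spurious gap (points) |
|---|---|---|---|---|
| 10% | 8% | 6% | 4% | 2 to 4 |
| 20% | 16% | 12% | 8% | 4 to 8 |
| 30% | 24% | 18% | 12% | 6 to 12 |

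For example, 0.20 × 0.80 = 16% against 0.20 × 0.40 = 8%. In 55 patients per arm that is 8.8 against 4.4 expected cases with no true difference.

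With the shares the other way, 60% in controls and 80% in the trial arm, the same true rates give 6% vs 8%, 12% vs 16% and 18% vs 24%. The gap is then 2 to 6 points against the trial arm. With 80% in both arms it is zero.

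**3. When BK is tested.** Table months are taken to run from conversion, and conversion to coincide with entry. Study test time after transplant = entry month + table month.

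| Entry month | Item 20 tests before or at entry | Study tests up to month 12 | Study tests after month 12, to 24 |
|---|---|---|---|
| 2 | none | 3, 5, 8, 11 | 14, 20 |
| 3 | 3 | 4, 6, 9, 12 | 15, 21 |
| 4 | 3 | 5, 7, 10 | 13, 16, 22 |
| 5 | 3 | 6, 8, 11 | 14, 17, 23 |
| 6 | 3, 6 | 7, 9, 12 | 15, 18, 24 |

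Three things follow.

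- Only patients entering at about month 2 have no scheduled BK test before or at entry.
- For them the Month 1 test falls at 2 + 1 = post-operative month 3, which is when item 20 gives controls their first test. Viremia acquired before month 2 is first seen at the same time in both arms.
- In the second post-transplant year trial patients have 2 to 3 scheduled BK tests. None is specified for controls, so a year-2 comparison would rest on unequal looking.

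**The case against.** The strongest reply is that 2m is one of 17 secondary objectives (a to q) in an unpowered pilot whose multiple comparisons are declared descriptive. Counting events that clinicians acted on matches 2k and 2l, which need hospitalization, and biopsy-defined BK nephropathy is captured separately in 2n. This limits the importance of the point but does not remove it. A descriptive rate must still mean the same thing in both arms. Objective 2n does not fill the gap either: biopsy is done only when rejection is suspected after a 25% rise in creatinine, so viremia without that rise is missed.

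Several stronger readings are tempting, and the documents do not support them.

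- *BK infection is hidden in the trial arm because immunosuppression has already been reduced.* The plan describes a lower calcineurin-inhibitor level with a change of second agent, and the background section states: "Combining everolimus and a calcineurin inhibitor gives rise to synergistic immunosuppressive properties". It does not say that total immunosuppression falls. Study Design item 11 also allows everolimus to be halved or interrupted, so trial patients still have something to reduce.
- *Early viremia is counted only against everolimus.* The timing in the working shows that controls carry the same early viremia into their first test.
- *BK is never tested until a month after conversion.* That is true of the visit table. Item 20, however, gives patients entering at months 3 to 6 a standard-care test before or at entry.
- *Scheduled tacrolimus reductions inflate the control count.* Read literally, 2m counts only reductions that a titer requires. What remains is a record-abstraction question when the two coincide.
- *If 5-10% are viremic at entry, 3 to 6 of 55 trial patients are miscounted.* 55 × 0.05 = 2.75 and 55 × 0.10 = 5.5, but a case also needs a dose cut. If half get one, the figure is 1.4 to 2.8, and lower again because not all 55 enter before a standard test.

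**Conclusion.** The definition is at fault. It depends on an open-label decision in one arm and on past practice in the other, so equal viremia can be counted unequally. Under the assumed inputs the artefact is 2 to 12 points in one direction or 2 to 6 in the other. Its sign and true size cannot be taken from the documents.

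The absent entry titer is a lesser weakness. It prevents a split into pre-existing and new infection for entrants at about month 2, but controls have the same gap, so its main effect is dilution.

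A reader might infer that 2m can never give a fair comparison. That goes too far: the objective is descriptive, and it can be repaired with tests that item 20 already provides. The conclusion assumes that item 20 was followed in the control era and that table months run from conversion.

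**What to change.** Redefine 2m as the first blood BK titer at or above one pre-stated threshold, whatever dose change follows. Choose a threshold that the assays of both eras can measure.

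- Apply it identically in both arms, from the same post-transplant index time, at post-operative months 3, 6, 9 and 12. State how study-visit titers map to those times, reconcile item 20 with the visit table, and report how many patients in each arm were tested at each time.
- Report trial-arm titers from year 2 descriptively, without a control comparison.
- Report titer-prompted dose reductions separately as a description, leaving out scheduled reductions.
- Do not drop patients positive at entry from one arm unless the same information exists in the other. At a month-2 matching date controls have no scheduled titer. Removing viremic trial patients while equally viremic controls stayed in would favour the trial arm. For the same reason, a Screening titer in the trial arm alone would not solve the problem. Where a pre-entry standard-care titer exists, show results with and without those patients as a sensitivity analysis.

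The cost is a change of endpoint wording and some abstraction of control records, with no added test. The comparison is confined to the first post-operative year, and some low-level viremia of little clinical consequence will count.
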